## 2. Objectives (include all primary and secondary objectives)

1. To assess the efficacy of the COach2Quit smoking cessation application by comparing smoking cessation rates at 2-weeks and 1-month among participants using the COach2Quit app and participants receiving brief anti-smoking advice (primary outcome is 1- month). *We hypothesize that the 1-month quit rate will be 20% in the COach2Quit arm and 10% in the brief anti-smoking advice arm.*

2. To evaluate whether the treatments differentially influence cognitive and behavioral processes related to cessation outcomes. Although formal mediational analysis is precluded by the moderate sample size in this pilot investigation, we will examine how treatments affect various intermediate variables assessed during and at the end of treatment including; (1) Urges to smoke; (2) Withdrawal symptoms; (3) Reinforcing Smoking Decisional Balance; (4) Smoking Abstinence Self-Efficacy; and, (5) Satisfaction with the program. *We hypothesize these measures will all benefit with COach2Quit compared to brief advice alone.*

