### **b. Secondary outcome variables**

1. Intermediate variables assessed at the end of treatment including; (1) Urges to smoke; (2) Withdrawal symptoms; (3) Reinforcing Smoking Decisional Balance; (4) Smoking Abstinence Self-Efficacy; and, (5) Satisfaction with the program among all participants

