### **c. Statistical plan including sample size justification and interim data analysis.**

#### **Data analysis plan**

**Overview** The primary outcome measure for the RCT is proportion of participants with biochemically verified smoking cessation as of 1-month; the primary exposure is study arm, brief-advice only vs. COach2Quit. We will compare proportions of smoking abstinence between study arms at 1-month.

Covariates of interest (e.g. sex, age, race, ethnicity, education, income, smoking history) will be assessed for relationship to prevalence of quitting. These comparisons will utilize the chi-square test for categorical variables and either the Student's t-test or the Wilcoxon signed rank test for continuous variables. Multivariate logistic models will be generated using forwards stepwise model selection, including study arm and all variables with  $p < 0.2$  or odds ratio  $< 0.5$  or  $> 2.0$  at the univariate level, ultimately generating the most parsimonious model.

We will conduct intent-to-treat analyses, providing the purest analysis for an RCT. For these analyses, participants who are lost to follow-up will be considered smokers from the date of last contact. This approach is conservative, as it will likely include participants who have not received either study intervention, but point estimates will be biased towards the null. This approach has been widely adopted in smoking cessation studies. We will compare rates of losses to follow up across the study arms, and look for differences in characteristics of those lost between the arms.

We will analyze number of smoke-free days obtained from questionnaires by comparing the proportions of smoke-free days between arms with a Wilcoxon signed rank test. We will estimate either the absolute difference in proportions, or after a  $\log(\text{days smoke-free}+1/\text{total days of follow up})$  transform if appropriate, with 95% confidence intervals. We will also measure durability of treatment effects using consecutive visits with biochemically verified smoking cessation.

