### **Sample Size**

Dated: 15 May 2017

This is a pilot RCT, thus our sample size is not powered to find significant differences between arms, but will provide estimates for future larger studies. We anticipate cessation rates of 20% in the COach2Quit arm and 10% in the brief-advice only arm at 1-month. We will enroll 150 participants into the study over 4 months, randomized 1:1.

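### The logistic model's covariates are chosen by an outcome-based screen and forward stepwise selection on about 22 expected quitters, with no stepwise entry level and no explicit statement that study arm is retained

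*Combined protocol and SAP*

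**What the plan says.** All of the modelling text is in section 7c, Data analysis plan.

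- **Main comparison.** "We will compare proportions of smoking abstinence between study arms at 1-month". Arm has a named role: "the primary exposure is study arm, brief-advice only vs. COach2Quit".
- **Candidates and screen.** "Covariates of interest (e.g. sex, age, race, ethnicity, education, income, smoking history) will be assessed for relationship to prevalence of quitting". The list is open, with seven variables given as examples. A variable passes on a univariate p below 0.2, or an odds ratio below 0.5 or above 2.0.
- **Model building.** "Multivariate logistic models will be generated using forwards stepwise model selection, including study arm and all variables with" those limits, "ultimately generating the most parsimonious model". The limits belong to the univariate screen. The stepwise step itself has no entry level, removal level or information criterion.
- **Rank.** The plan does not say how the logistic models stand relative to the comparison of proportions.
- **Size.** The Sample Size section plans 150 participants, 1:1, with expected cessation of 20% and 10%. It says that "our sample size is not powered to find significant differences between arms" and that the aim is to supply estimates for larger studies.

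**Secondary scales.** Section 2 says "we will examine how treatments affect various intermediate variables assessed during and at the end of treatment", and section 7b lists "Intermediate variables assessed at the end of treatment including" urges, withdrawal, decisional balance, self-efficacy and satisfaction. Section 7c gives no analysis for these five measures.

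**The concern.** Screening covariates on the trial's own outcome and then stepping through the survivors makes the final model depend on chance, especially with few events. Three gaps add to this. The candidate list is open. The stepwise entry level is unstated, so different analysts could reach different models from the same data. The sentence on model building lists arm beside the screened variables without saying that it is kept.

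The odds ratio limits raise a further problem. They admit rare categories easily, because those odds ratios are the noisiest. If they also apply to continuous variables, they depend on the unit chosen.

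At stake is the value of the adjusted model as an estimate to carry into a larger trial: which covariates it contains and how strong they appear. The arm effect would be at stake only if arm itself had to earn entry.

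**Working it through.** **1. Expected events (from the Sample Size section).** 75 × 0.20 + 75 × 0.10 = 15 + 7.5 = 22.5 quitters. Losses are counted as smokers and add no events. Events per model term:

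- arm plus the seven named covariates at one term each: 22.5 / 8 = 2.8
- arm plus two: 22.5 / 3 = 7.5
- arm plus one: 22.5 / 2 = 11.25

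The plan states no event count or power, so there is no figure of its own to reproduce.

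**2. Unadjusted comparison.** At the planned rates the difference is 10 points, with 95% half-width 1.96 × √(0.20 × 0.80/75 + 0.10 × 0.90/75) = 11.3. The interval is −1.3 to 21.3. No covariate selection enters it.

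**3. The procedure simulated, arm forced in.** The steps were a univariate screen (t-test or chi-square p < 0.2, or OR < 0.5 or > 2.0), then forward likelihood-ratio selection. From the documents: 75 per arm, 20% and 10%. *Assumed:* 7 covariates (3 continuous; 4 binary with prevalence 50, 30, 20 and 10%), 2 of them related to quitting at OR 1.5 per SD, and three possible entry levels. 5,000 trials.

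| Entry level | 0.05 | 0.10 | 0.20 |
|---|---|---|---|
| At least one unrelated covariate in final model | 26% | 44% | 64% |
| At least one real predictor missing | 84% | 73% | 62% |
| Mean OR shown for a selected predictor (true 1.5) | 1.98 | 1.89 | 1.81 |
| Two trials select the same covariate set | 15% | 8.5% | 5% |
| Median arm OR (2.37 if the two real predictors are pre-specified) | 2.37 | 2.39 | 2.40 |

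Sensitivity to the assumed OR (3,000 trials each):

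- OR 1.25: unrelated covariate in 26 / 44 / 65%; real predictor missing in 98 / 95 / 90%.
- OR 2.0: unrelated covariate in 25 / 42 / 59%; real predictor missing in 38 / 26 / 18%.

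**4. Type I error and power for arm, arm forced in.** With no arm effect (15% in both arms) and two related covariates, type I error was 5.7 / 5.8 / 5.6% against 5.1% pre-specified. With no related covariate it was 4.7 / 4.8 / 4.8% against 4.8%. In a run of 3,000 trials with a slightly different covariate mix, power was 40.0 / 40.4 / 39.8% for stepwise, 39.3% with the two real predictors pre-specified and 37.5% with two uninformative ones. These differences are negligible.

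**5. If arm had to earn entry.** Arm is dropped in 59 / 46 / 36% of simulated trials, with median OR when kept of 3.7 / 3.4 / 3.1, against 2.25 implied by the planned rates: (0.20/0.80) / (0.10/0.90). Exact enumeration of the two arms without covariates gives 59 / 46 / 31% dropped.

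**6. The odds ratio limits.** For an unrelated category, n = 150 and a 15% quit rate, the OR rule alone passes 40 / 25 / 19 / 15% at prevalence 10 / 20 / 30 / 50%. The p < 0.2 rule passes about 20% throughout. On units, an OR of 2.0 per decade of age is 2.0^(1/10) = 1.07 per year.

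**7. Secondary scales.** With equal variances and baseline–follow-up correlation r (*assumed*, not in the documents), ANCOVA cuts variance by r² against follow-up scores alone and by 1 − (1 − r²)/(2(1 − r)) against change scores. At r = 0.3 / 0.5 / 0.7 this is 9 / 25 / 49% and 35 / 25 / 15%.

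**The case against.** The strongest reply is that this hardly touches the trial's question. The quit proportions are compared without a model. Arm is the named primary exposure and stands apart from the screened variables, so it is most naturally read as always included, and step 4 shows that its inference then barely moves. Covariate odds ratios are not an objective or a listed outcome, and this is an unpowered pilot. All of that stands, and it limits the severity.

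The percentages also depend on the assumptions. For five unrelated covariates, 1 − (1 − entry level)⁵ already gives 23 / 41 / 67%, close to the simulated 26 / 44 / 64%. That is fair, but it is also the point: the answer depends on an entry level that the plan leaves out.

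A reader might infer that the search costs precision for arm, since the SD of its log OR is 0.563 to 0.567 under stepwise and 0.554 under the pre-specified model. This does not follow. In logistic regression that SD rises when real predictors are added: it is 0.537 with two uninformative covariates and 0.554 with the two real ones, yet power is higher with the latter (39.3% against 38.3%).

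Two limits apply to the smaller points. Section 7c tests continuous variables by t-test or Wilcoxon, so the OR limits may be meant only for categories; the text does not say. The Initial Assessment text in section 4a describes baseline items by topic and does not confirm that they are the same scales as at follow-up.

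**Conclusion.** The concern holds for the covariate part of the logistic model, at low to moderate severity. The procedure would often include unrelated covariates, often miss real ones, and overstate those it selects. The sizes rest on the assumed number and strength of covariates and the assumed entry levels. The direction held over the ranges tried, although the share of trials missing a real predictor fell to 18 to 38% at a true OR of 2.0.

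A reader might infer that the primary result is compromised or that the plan intends to let arm drop out. The documents support neither: the comparison of proportions needs no model, and the wording on arm is ambiguous at most. Only if arm had to earn entry would its adjusted effect often be absent, and too large when shown. Much of that absence would reflect the low power that the plan concedes.

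The missing analysis for the secondary scales is a real but separate gap.

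**What to change.** **Main change.** Replace the screen and the stepwise step with one pre-specified logistic model. Study arm is always in, with one or two baseline covariates named in advance with their units. The choice is the sponsor's; the number is kept small because about 22 events are expected. Report the model beside the unadjusted risk difference with its 95% CI. Label any search for predictors of quitting exploratory.

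**Secondary scales.** Where the sponsor confirms that the same scale is used at baseline and follow-up, compare arms by ANCOVA on the baseline score. The Initial Assessment text suggests this for urges, withdrawal, decisional balance and confidence to quit. Compare satisfaction, which has no baseline value, unadjusted.

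**Cost.** Wording only, with no new data. The downside is that a covariate named in advance may prove uninformative. In the simulations that cost about one to two points of power (39.3% to 38.3% in one run, 39.3% to 37.5% in the other).

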**f. Definition of treatment failure or participant removal criteria.**

Participants will be discontinued from the study if they (1) ask to be removed from the study (2) are found to be using other smoking cessation treatments (3) develop a medical condition precluding the use of the iCO monitor such as COPD (4) develop a serious adverse event (SAE).

**g. Description of what happens to participants receiving therapy when study ends or if a participant's participation in the study ends prematurely.**

The participant will continue to receive care at these facilities should he/she choose to leave the study for any reason. If a participant leaves the study prematurely due to an adverse event, text messages will stop being sent to them.

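### Counting those lost as smokers does not guarantee bias towards the null, and no sensitivity analysis by arm is planned

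*Combined protocol and SAP*

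**What the plan says.** The relevant text is the intent-to-treat paragraph of the data analysis plan in section 7c. It sets the missing-outcome rule: "participants who are lost to follow-up will be considered smokers from the date of last contact". The next sentence opens "This approach is conservative, as it will likely include participants who have not received either study intervention" and ends "but point estimates will be biased towards the null". No condition is attached, and the paragraph then notes that the approach is in common use in this field.

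For losses, the plan will compare rates between arms and "look for differences in characteristics of those lost between the arms". It describes no analysis that re-estimates the treatment effect under a different assumption about missing outcomes.

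The sample size section says the trial is "not powered to find significant differences between arms, but will provide estimates for future larger studies".

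**The concern.** It is unclear what the claim of conservatism refers to. The reason given, that people who received neither intervention are included, describes dilution under intent-to-treat. But the sentence directly before it is the smoker rule, and the remark about common use in cessation studies fits that rule. A reader can fairly take the claim to cover the rule.

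Read that way, it claims more than the rule delivers. Coding every lost participant as a smoker lowers the observed quit rate in both arms. Whether the contrast shrinks or grows depends on which arm loses more quitters.

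This matters because the trial's stated product is estimates for later studies. Someone planning the next trial who is told that the estimate is biased towards the null may treat it as a floor. The trial is open label and only one arm receives the monitor and app, so unequal loss is possible. The documents do not settle which arm would lose more.

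**Working it through.** **Inputs from the documents.** Sample size section: "We anticipate cessation rates of 20% in the COach2Quit arm and 10% in the brief-advice only arm at 1-month", and 150 participants randomised 1:1, so 75 per arm.

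**Assumptions.** The documents state no loss rates and no significance level for the arm comparison. Loss is written app/control. A two-sided 5% chi-square test without continuity correction is assumed. The plan gives no figure of its own on this point to reproduce.

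**Formula.** Let p be an arm's true quit rate, d the share lost, and a the true quit rate among those lost. Under the smoker rule the observed rate is p − d·a. With subscript 1 for the app and 0 for control, the bias in the risk difference (RD) is

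d0·a0 − d1·a1.

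If everyone lost really smokes (a = 0 in both arms), there is no bias. If those lost quit at their arm's rate (a = p), the observed rate is p(1 − d).

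**Planned rates, a = p.** True values: RD 10 points; odds ratio (OR) (0.20/0.80)/(0.10/0.90) = 2.25.

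| Loss app/control | Observed rates | RD (points) | OR | Direction |
|---|---|---|---|---|
| 20%/20% | 16.0% vs 8.0% | 8.0 | 2.19 | towards the null |
| 10%/15% | 18.0% vs 8.5% | 9.5 | 2.36 | RD towards, OR away |
| 10%/25% | 18.0% vs 7.5% | 10.5 | 2.71 | away on both scales |
| 25%/10% | 15.0% vs 9.0% | 6.0 | 1.78 | towards the null |

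**Thresholds.** The RD is unbiased when 0.20·d1 = 0.10·d0, so it is inflated only if control loss exceeds twice app loss. The OR is more sensitive. With 10% app loss the observed app odds are 0.18/0.82 = 0.2195. An OR of 2.25 then needs control odds of 0.0976, a rate of 8.89%, which is control loss of 11.1%. With 20% app loss the same steps give 22.0%. The OR is relevant because the plan includes study arm in logistic models.

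**Those lost quit at half their arm's rate, 10%/25%.** Observed 19.0% vs 8.75%: RD 10.25 points, OR 2.45.

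**No true effect, 15% in both arms, 10%/25%.** Observed 13.5% vs 11.25%, a spurious +2.25 points. Exact binomial enumeration with 75 per arm gives 7.0% two-sided rejection, against 5.1% with no loss. If those lost quit at half the rate (14.25% vs 13.125%), the figures are 1.1 points and 5.5%.

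**Is the smoker rule a floor?** Let the quit rate among those lost range from 0 to 20% in the app arm and 0 to 10% in control, so no higher than planned.
- At 10%/25%: lowest 0.18 − (0.075 + 0.25 × 0.10) = 8.0 points; highest (0.18 + 0.10 × 0.20) − 0.075 = 12.5 points. The smoker rule gives 10.5.
- At 20%/20%: lowest 0.16 − (0.08 + 0.20 × 0.10) = 6.0 points; highest (0.16 + 0.20 × 0.20) − 0.08 = 12.0 points. The smoker rule gives 8.0.

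The rule is not the lower end in either case.

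**Scale.** At 10%/25% the expected losses are 7.5 and 18.75 people, hiding 7.5 × 0.20 = 1.5 and 18.75 × 0.10 ≈ 1.9 quitters. The standard error of the RD is √(0.18 × 0.82/75 + 0.075 × 0.925/75) = 0.054, or 5.4 points.

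**The case against.** The strongest reply is that the sentence was never about the smoker rule. Its only stated reason concerns people who received neither intervention, which is the usual account of intent-to-treat dilution and is unremarkable on that reading. The common-use remark could fit intent-to-treat as well. This stands as far as it goes: the wording is ambiguous, and if only dilution was meant, a clarifying phrase settles that half. The plan would still say nothing on how the estimate responds to missing outcomes.

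Second, the loss rates are invented. Both arms share the visit schedule, weekly calls, vouchers (the largest at the last visit) and short follow-up, all of which work against unequal loss. Fair: 10%/25% is a stress case, not a forecast. These features do not rule out imbalance in an open-label trial.

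Third, the shifts are small, and on the risk difference the plan's statement survives moderate imbalance. The low ends of the ranges above also need an unfavourable combination: no lost app user quits while lost controls quit at the full planned rate. This is accepted and limits the severity. The rejection rates likewise carry little weight in a trial not powered for significance.

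Fourth, the plan already compares losses by arm, and a reader with the counts could build the grid. The comparison is a useful diagnostic, but no analysis is tied to it, so any later choice of analysis would be made after seeing the data.

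**Conclusion.** The concern holds, as a minor point. Applied to the smoker rule, the unconditional statement about direction is wrong as written: the bias has no fixed sign. With equal loss, and those lost quitting at their arm's rate, the statement is right at the planned rates. With control loss more than twice app loss it fails on the risk difference, and a much smaller imbalance is enough on the odds ratio. That no passage plans a sensitivity analysis by arm does not depend on how the ambiguous sentence is read.

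The sizes rest on assumed loss rates and on assumed quitting among those lost. They illustrate the dependence and do not predict the bias in this trial. What is established is an unsupported claim about direction, in a pilot whose main output is a point estimate.

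**What to change.** 1. In section 7c, replace the claim of conservatism and bias towards the null with a statement that, under the smoker rule, the direction depends on loss, and on quitting among those lost, in each arm. If only intent-to-treat dilution was meant, say so.
2. Keep the smoker rule for the main analysis. Pre-specify a sensitivity analysis that varies the quit rate among participants with missing outcomes separately by arm: either a grid from 0% up to at least the rate observed among those followed in that arm, or multiple imputation.
3. While editing, state that participants discontinued under section 4f stay in their randomised arm and that those with missing outcomes enter this analysis. Intent-to-treat already implies the first part; this is missing detail and not part of the verdict.

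The cost is one or two sentences for each item and a few hours of analysis on data already collected, with no extra visits. The drawback is that the result can no longer be called conservative by construction.

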## **4. Study Procedures**

### **a. Study design**

**Overview:** The goal of this randomized controlled trial is to assess the efficacy of the novel COach2Quit smartphone application by determining whether the use of this app reduces smoking more than brief anti-smoking advice alone. This will be a two-arm individually randomized trial and participants who are currently smoking will be assigned 1:1 to either study arm. Smoking behavior will be measured through self-report at baseline, 2-week and 1-month follow up visits. Smoking behavior will also be verified by 2 biomarker measurements: carbon monoxide breath test and urine cotinine, collected at baseline, 2-week and 1-month follow-up visits. In addition, participants will receive weekly follow-up calls. **The primary outcome will be smoking cessation at the 1-month follow-up visit.**

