**c. Blinding, including justification for blinding or not blinding the trial, if applicable.**

This will be an open-label trial in which neither the subjects nor the study coordinator will be blinded as to treatment assignment after randomization. However, the study interviewer conducting baseline breath CO and urine testing will be blinded as to treatment arm of the individual participants to decrease bias.

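### The smoke-free-days analysis in section 7c does not use the same-visit CO and cotinine results, so claims of full abstinence that those tests contradict are counted in full

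*Combined protocol and SAP*

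**What the plan says.** Section 7c (Data analysis plan) takes the day count from self-report: "We will analyze number of smoke-free days obtained from questionnaires by comparing the proportions of smoke-free days between arms". It promises an estimated difference with a 95% confidence interval. It gives no rule for a participant whose reported days disagree with a test at the same visit.

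Two other analyses under the same heading are verified. The primary outcome is the "proportion of participants with biochemically verified smoking cessation as of 1-month", and for persistence of effect the plan says: "We will also measure durability of treatment effects using consecutive visits with biochemically verified smoking cessation". The smoke-free-days analysis carries no such qualifier.

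The verifying data exist. Section 4a states: "Smoking behavior will be measured through self-report at baseline, 2-week and 1-month follow up visits". It continues: "Smoking behavior will also be verified by 2 biomarker measurements: carbon monoxide breath test and urine cotinine". Those tests are scheduled at the same three visits.

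On blinding, section 4c says that "neither the subjects nor the study coordinator will be blinded as to treatment assignment after randomization". It adds that "the study interviewer conducting baseline breath CO and urine testing will be blinded as to treatment arm".

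Sections 7a and 7b, which list the primary and secondary outcome variables, do not include smoke-free days.

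**The concern.** Section 4a presents the biomarkers as a check on smoking behavior in general, but section 7c applies that check to two analyses and is silent on the third. A participant who reports no smoking since the last visit and tests positive that day would fail the verified primary outcome at 1 month, yet score a fully smoke-free interval in this analysis.

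Reporting could also differ by arm. Under Initial Assessment in section 4a, app users are told that each reading goes to the study team, and they answer questions about the amount smoked. Under section 6 they receive praise or encouragement tied to their CO result. Controls have none of this. Monitoring might deter false claims in the app arm, or engagement might encourage them; the documents do not settle which.

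The Sample Size paragraph says the pilot is meant to supply estimates for larger studies. A difference in smoke-free days could be carried forward for that purpose, and without counts of contradicted reports by arm a reader could not tell a smoking difference from a reporting difference.

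**Working it through.** The plan gives no effect size, variance or power for this analysis, so there is no figure to reproduce. The check covers what the tests can contradict and how large a reporting difference could be.

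**Inputs from the documents**
- 150 participants randomized 1:1, so 75 per arm (Sample Size).
- Anticipated 1-month quit rates of 20% and 10% (Sample Size), so the average non-quit rate is (80% + 90%) / 2 = 85%.
- Cotinine is detectable for 2 to 4 days after use (section 6, Urine Cotinine Test).
- CO of 10 ppm or less indicates abstinence (section 6, Carbon Monoxide Breath Test).
- Participants lost to follow-up count as smokers from last contact (section 7c).

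**Assumed**
- Total follow-up of 28 to 30 days, with intervals of about 14 days.
- All misreporting rates, and the standard deviation used in step 4.

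**1. Is the gap closed elsewhere?** The loss-to-follow-up rule covers people who stop attending. It does not cover someone who attends, reports no smoking and tests positive. No other rule alters reported days.

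**2. Share of follow-up that a positive cotinine bears on** (window / follow-up)
- One visit: 2/30 = 6.7% to 4/28 = 14.3%.
- Both follow-up visits: 4/30 = 13.3% to 8/28 = 28.6%.

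A positive test therefore contradicts a claim of no smoking at all in the interval, but it says nothing about most of the individual days.

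**3. Spurious difference in mean proportion** (excess misreporters × over-claimed days / 28)
- 2 to 4 days over-claimed, 5% to 20% more misreporters in one arm: 0.05 × 2/28 = 0.4 points to 0.20 × 4/28 = 2.9 points.
- 14 days over-claimed, same excess: 0.05 × 14/28 = 2.5 points to 0.20 × 14/28 = 10 points.

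Each falsely claimed 14-day interval moves its arm's mean by (14/28)/75 = 0.67 points, so the count of contradicted intervals by arm translates directly into a possible shift.

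**4. Against sampling error, on assumed inputs only.** Suppose 5% of non-quitters in one arm and 15% in the other falsely claim the whole period, moving from 0% to 100% smoke-free.
- Difference: 0.85 × (0.15 − 0.05) = 8.5 points.
- With an assumed standard deviation of 0.35, SE = 0.35 × √(2/75) = 5.7 points, so the ratio is 8.5/5.7 = 1.5.
- If only one of two intervals is falsely claimed, the difference is 8.5 × 14/28 = 4.25 points, or 4.25/5.7 = 0.7 SE.

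**The case against.** The strongest reply is that a count of days and verified abstinence at a visit measure different things. Someone who lapses the day before the 1-month visit correctly fails the primary outcome and can correctly have many smoke-free days. Cotinine looks back only 2 to 4 days, so most days between visits cannot be verified with these tests and self-report is the only practical source. This stands. It is why the questionnaire count should remain the stated analysis, and why only claims of no smoking in the interval should be treated as contradicted.

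A second reply is that the visit check is the same in both arms: everyone gives breath and urine samples, sees the results immediately and is counseled if positive. This also stands, and it weakens any confident claim of differential reporting. It does not remove the daily monitoring that only the app arm has.

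Some stronger readings are tempting, but the documents do not support them:
- That the plan decided to credit contradicted days. It does not say so. Section 4a states a general intention to verify, and section 7c omits how that applies here. Full counting is what results if 7c is run as written.
- That a positive test discredits every claimed day. The 2-to-4-day window rules this out.
- That nobody is blinded. Section 4c blinds the interviewer for baseline CO and urine testing. It is silent on follow-up testing.
- That this is the only graded smoking measure. The durability analysis across consecutive visits is another, and it is verified.

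**Conclusion.** The concern holds in a limited form. An added analysis uses open-label self-report, the verification available at the same visits is not carried into it, and claims of full abstinence contradicted by a same-visit test are counted in full when 7c is applied as written.

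The size and direction of any arm difference are unknown. The range of 0.4 to 10 points, and the 8.5-point case at 1.5 SE, rest on assumed misreporting rates, assumed follow-up length and, for the SE, an assumed standard deviation. They show what could happen and are not estimates. A reader might infer that the trial's main result is at risk. It is not: the primary outcome and the durability analysis are both biochemically verified, smoke-free days are in neither outcome list, and the plan says the pilot is not powered to find differences between arms. This is a worthwhile small improvement, not a defect in the main comparison.

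**What to change.** Keep the questionnaire count as the stated analysis and add the following to section 7c:

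1. A sensitivity analysis that credits no smoke-free days for any interval (baseline to 2 weeks, 2 weeks to 1 month) in which the participant reports no smoking but CO is above 10 ppm or urine cotinine is positive at the closing visit.
2. A table of these contradicted self-reports by arm and interval, with CO-positive and cotinine-only cases separate. The separation matters because section 6 notes that nicotine replacement also produces cotinine.

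Recoding every day inside a 4-day cotinine window is not recommended. A positive result shows some use in the window, not use on each day. The recode needs dated days, whereas 7c describes a number of days. It would also remove at most 4/14 = 29% of a false two-week claim.

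The cost is a few lines of programming, using the count for each interval and the visit tests already scheduled. The count must be held separately for the two intervals. The main downside is that the sensitivity analysis can discard genuine smoke-free days, up to a whole interval for an affected participant. It also leaves partial over-claims untouched, since a positive test does not contradict someone who reports some smoking. Writing the rule before analysis avoids a choice made after the data are seen.

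### The plan names the Wilcoxon signed rank test, a paired test, for two comparisons of independent groups; the rank-sum test is needed in both places

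*Combined protocol and SAP*

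**What the plan says.** The signed rank test appears twice in section 7c, Data analysis plan.

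- **Covariates.** Participant characteristics such as age and smoking history "will be assessed for relationship to prevalence of quitting". The tests offered are chi-square for categorical variables, and either Student's t-test or "the Wilcoxon signed rank test for continuous variables".
- **Smoke-free days.** The plan describes "comparing the proportions of smoke-free days between arms with a Wilcoxon signed rank test". No other test is named for this measure. An absolute difference, or a difference after a log transform, is to be reported with a 95% confidence interval.

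Section 4a describes the design: "This will be a two-arm individually randomized trial", with 1:1 assignment. Section 7c (Sample Size) sets enrolment at 150. Neither section, nor any other, describes matching, crossover or a within-person contrast for these two comparisons. The rank-sum test is not named anywhere.

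**The concern.** The signed rank test takes one difference per matched pair, ranks the absolute differences and compares the positive ranks with the negative ones. Independent groups have no natural pairs. Two things can then happen.

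- **Groups of unequal size:** some participants have no partner, and the statistic is not defined.
- **Groups of equal size:** software will pair row 1 with row 1, row 2 with row 2, and so on. The p-value then depends on how the data set happens to be sorted.

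For smoke-free days the signed rank test is the only test named, so a literal reading leaves no well-defined pre-specified test, and the choice would have to be made later. For covariates, the non-parametric option offered beside the t-test could not be used.

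**Working it through.** The plan gives no derived figure to reproduce here. The check is whether the named test can be computed on the groups the plan will produce and, if so, whether it gives one answer.

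**Inputs**

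- Enrolment of 150, allocated 1:1 (section 7c, Sample Size), which is 75 per arm if exactly balanced.
- Expected quit rates, same section: "We anticipate cessation rates of 20% in the COach2Quit arm and 10% in the brief-advice only arm at 1-month".
- Losses to follow-up (section 7c, Data analysis plan): "participants who are lost to follow-up will be considered smokers from the date of last contact". They therefore stay in the analysis.

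**Covariates: quitters against non-quitters**

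- Expected quitters: 75 × 0.20 + 75 × 0.10 = 15 + 7.5 = 22.5.
- Expected non-quitters: 150 − 22.5 = 127.5.
- Quitters are distributed as Bin(75, 0.20) + Bin(75, 0.10). The exact 2.5th and 97.5th percentiles are 14 and 31.
- The signed rank test needs 75 against 75. The probability of exactly 75 quitters is 1.8 × 10⁻²⁴.
- If a much higher common quit rate of 40% is assumed, P(Bin(150, 0.4) = 75) = 0.0030, or 0.3%.

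A standard signed rank routine given 22 and 128 values returned an error.

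**Smoke-free days: arm against arm**

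The documents say only that allocation is 1:1, so the chance of equal arms depends on an assumption.

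- Simple randomisation: P(75 against 75) = C(150, 75) / 2¹⁵⁰ = 0.065.
- A completed blocked list: close to 100%.

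Because losses are counted as smokers and kept, dropout need not unbalance the arms. With 74 against 76 the routine again returned an error.

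**Equal arms: does the answer depend on row order?**

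The following values are made up, six per arm, and show only that the dependence exists. Arm A has 0, 5, 10, 15, 20, 25 smoke-free days; arm B has 2, 7, 12, 17, 22, 27.

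| Row order | Differences B − A | Test | Two-sided exact p |
|---|---|---|---|
| Both ascending | +2 six times | Signed rank | 2/64 = 0.031 |
| B reversed | 27, 17, 7, −3, −13, −23 | Signed rank, W = 1 + 3 + 5 = 9 | 0.84 |
| Any order | not used | Rank-sum, U = 21 | 0.70 |

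The first row is an extreme case, because sorting both arms by outcome forces every difference to +2. A less contrived illustration used one simulated data set with 75 per arm and assumed beta distributions. Over 2000 random pairings the signed rank p-value ran from 0.018 to 0.350, with a median of 0.126. The rank-sum test gave a single p of 0.035.

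**The case against.** The strongest reply is that this is a slip of the pen with almost no practical effect. Both uses are plainly two-group comparisons, and one sits beside Student's t-test, which most readers would take as the unpaired version. For covariates the error would announce itself, since software refuses unequal groups, so a wrong result could not pass unnoticed.

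Nor is there a false-positive problem in the equal-arms case. If the pairing is unrelated to outcome and the arms do not differ, the differences are symmetric about zero and the test keeps about its nominal size. A simulation with 75 per arm and the same assumed beta(0.6, 1.5) distribution in both arms gave 5.5% rejections at a nominal 5%. Against an assumed beta(0.85, 1.5) alternative, power was 43%, compared with 51% for rank-sum.

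Much of this stands, and it sets the weight of the point. What remains is that the written plan names a test that does not fit either comparison. For smoke-free days it names no other. With equal arms the software would not object, and the reported p-value would be one arbitrary draw from a range, with some loss of power.

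**Conclusion.** The point holds and is minor. Followed literally, the covariate option cannot be run. The smoke-free-days test either cannot be run (unequal arms) or gives a p-value that depends on row order (equal arms). The covariate conclusion rests only on the plan's own rates and survives a far higher assumed quit rate. For the arms, which of the two failures occurs depends on the unstated allocation method.

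The reach is limited:

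- The primary 1-month quit-rate comparison, the chi-square and t-test options, and the route into the model by odds ratio are unaffected.
- Smoke-free days is not in the primary list (section 7a). The secondary list (section 7b), which begins "Intermediate variables assessed at the end of treatment including", does not include it either.
- The Sample Size text says that "our sample size is not powered to find significant differences between arms".
- Nothing ties the smoke-free-days estimate or its confidence interval to the signed rank test, although the method for the interval is not stated.
- The plan does not say whether a Wilcoxon p-value feeds the p < 0.2 screen, so no effect on the logistic model is claimed.

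**What to change.** In section 7c, Data analysis plan, replace *signed rank* with *rank-sum (Mann-Whitney)* in both places: the covariate comparisons and the smoke-free-days comparison. Each can then be computed whatever the group sizes, with one p-value that does not depend on row order. The cost is two wording changes. Sample size, data collection and trial conduct stay as they are, and this point requires no other change.
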